7.3.4 General Medical History

The number and percentage of subjects with any relevant medical history and by body system will be presented, overall and by treatment group.

By subject listings of medical history will be provided. A by subject listing of pregnancy test data will also be provided.

7.3.5 Baseline Safety Laboratory Tests

Baseline safety laboratory evaluations will be the last available samples taken on or before Cycle 1, Day 1 and within 60 days of randomization.

Baseline safety laboratory values will be presented by CTC severity grade, by treatment group. Separate tables will be generated for hematology (hemoglobin, WBC, ANC [neutrophils plus bands], ALC [absolute lymphocyte count] and platelets, liver function (ALT, AST, alkaline phosphatase, albumin, direct bilirubin and total bilirubin) and renal function/electrolytes (sodium, potassium, bicarbonate, calcium, glucose, and creatinine, creatinine clearance < 60 ml/min, ≥ 60 ml/min). Sodium, potassium, calcium, and glucose will be presented separately, based on their high and low values.

CTC grades will be derived as part of the analysis data set programming using version 3.0.

7.4 Extent of Exposure

7.4.1 Study Therapy

Lenalidomide, oral dexamethasone and IV dexamethasone are given at fixed doses and are not adjusted for body surface area or weight. The elotuzumab dose, in contrast, is adjusted for weight. Throughout this SAP, a subject's elotuzumab dose level at a particular time point will refer to the actual dose, in mg/kg, rather than their planned dose. A subject's actual elotuzumab dose level will be computed by dividing their total dose delivered, in mg, as recorded on the "Record of Study Medication - Elotuzumab" eCRF page, by their latest pre-dose weight, in kg, on Day 1 of that cycle.

7.4.1.1 Duration of Study Therapy

The number of cycles of treatment received by subjects will be summarized (using n, mean, STD, median, min, max, q1 and q3) by treatment group.

The duration of each treatment (elotuzumab, dexamethasone [oral, IV, and oral and IV combined] and lenalidomide), in months, will be calculated as:

$$(date\ of\ last\ dose\ of\ the\ drug - date\ of\ first\ dose\ of\ the\ drug + 1) / 30.4375$$

Duration of each of the study treatments will be summarized by treatment group.

7.4.1.2 Dose Modifications

Elotuzumab:

- **Dose Reduction**

Reduction of Elotuzumab dosing is not permitted as per the protocol.

- **Dose Delay**

A delay for Elotuzumab will be computed based on records from the dosing CRF page. A delay in Elotuzumab dosing will be defined as the number of days from the start date of the previous infusion to the start date of the current infusion being > 8 days and ≤10 days (if in cycles 1, 2 or first infusion of cycle 3) or > 15 days and ≤ 21 days (from second infusion of cycle 3 - cycle 19) or > 29 days and ≤ 35 days (from cycle 20 onwards).

For courses with a delay of Elotuzumab infusion, the time of delay in infusion will be summarized in the categories: 2 - 3 days, 4 - 7 days.

The number and percentage of subjects with any dose delay, with 1, 2, 3, or ≥ 4 reported delays will be summarized. For subjects with a delay, their reason for delay (from the dose modification page of the CRF) will be summarized in the groups: "hematologic toxicity", "non-hematologic toxicity", "AE", "dosing error" and "other". For subjects without an available reason for delay, the category "unknown" will be used.

A by-subject listing for dose delay will be presented for all treated subjects. This listing will include all reported delays per CRF, regardless of whether the subject had a computed delay based on the actual dosing dates.

- **Dose Omission**

An omission for Elotuzumab will be calculated based on records from the dosing CRF page. If the interval between the two dosing dates for Elotuzumab is >10 days (in cycles 1, 2 or first infusion of cycle 3) or >21 days (from second infusion of cycles 3-19), or > 35 days from cycle 20 and beyond, the dose will be considered to have been omitted.

For courses with an omission of Elotuzumab infusion, the time between the previous and current infusion will be summarized in the categories: 11 - 14, 15 - 21, 22 - 27, 28 - 35, \geq 36 days.

The number and percentage of subjects with a dose omission, and with 1, 2, 3, or \geq 4 omissions will be summarized. For subjects with an omission, their reason for omission (from the dose modification page of the CRF) will be summarized in the groups: “hematologic toxicity”, “non-hematologic toxicity”, “AE”, “dosing error” and “other”. For subjects without an available reason for omission, the category “unknown” will be used.

A by-subject listing for dose omission will be presented for all treated subjects. This listing will include all reported omissions per CRF, regardless of whether the subject had a computed omission based on the actual dosing dates.

- **Dose Interruption**

The number and percentage of subjects with any interruption in their elotuzumab infusion, with 1, 2, 3, or \geq 4 interruptions, with an interruption due to “infusion reaction”, “infusion administration issues” and “other” will be presented. In addition, duration of interruptions (in minutes) will be summarized via descriptive statistics.

A by-subject listing will be generated for elotuzumab IV interruptions. This listing will include reason for interruption, whether the infusion was resumed, and duration of the interruption.

- **IV Rate Reduction**

The number and percentage of subjects with any elotuzumab IV rate reduction, with 1, 2, 3, or \geq 4 rate reductions, and with rate reductions due to “infusion reaction,” “infusion administration issues,” and “other” will be presented.

A by-subject listing will be generated for elotuzumab IV rate reductions.

Lenalidomide:

- **Dose Reduction**

Reduction of Lenalidomide will be computed based on the actual dose received. In any study day (excluding, cycle 1, day 1), the drug will have a calculated reduction compared to the previous day, if the actual level of the administered dose is below the actual level of the administered dose in the previous instance. The information for this analysis will be derived programmatically, using the total daily dose on the “Record of Study Medication - lenalidomide” eCRF page.

The daily dose levels are defined as follows:

- Dose level 0 or full dose (25 mg): \geq 20.0
- Dose level -1 (15 mg): 12.5 mg to < 20.0

- Dose level -2 or starting dose for moderate renal impairment (10 mg): 8.75 to < 12.5 mg
- Dose level -3 for subjects with severe renal impairment (15 mg every 48 hours): 6.25 to < 8.75 mg
- Dose level -4 for subjects with End Stage Renal Disease (ESRD) (5 mg): < 6.25 mg

The number and percentage of subjects with a dose reduction, and the lowest dose level achieved per subject (-1, -2, -3, \leq -4), will be presented by treatment group. This table will be broken out by whether the subject started at the standard dose level or at the 10 mg dose level.

The reason for dose reduction as reported by the investigator will be tabulated for all instances with a calculated reduction based on the dose modification for Lenalidomide page. A category “unknown” will be defined for all calculated reductions with no reason reported by the investigator.

A by-subject listing of dose reductions will be generated. This will include all reported reductions per investigator, regardless of whether it met the requirements for a calculated reduction.

- **Dose Interruption**

In any cycle, the Lenalidomide dose will be considered as interrupted if there is a gap of two or more days between two dosing dates within that cycle where the subject did not receive the study drug. This will be calculated based on the information from the dose modification CRF for Lenalidomide.

The number and percentage of subjects with dose interruption, with 1, 2, 3, or \geq 4 reported interruptions will be presented. For subjects with a computed interruption, their reason for interruption will be summarized from the dose modification CRF. For subjects without an available reason for interruption, the category “unknown” will be used.

Dexamethasone (IV) and Oral:

For IV dexamethasone the following summaries will be provided:

- The number of subjects with any dose delay, with 1, 2, 3, or \geq 4 reported delays, and with a reason for delay of “hematologic toxicity”, “non-hematologic toxicity”, “AE”, “dosing error” and “other”.
- The number of subjects with any reported dose omission, with 1, 2, 3, or \geq 4 reported omissions, and with a reported reason for omission of “hematologic toxicity”, “non-hematologic toxicity”, “AE”, “dosing error” and “other”.
- The number of subjects who discontinued the study drug, and reason for the discontinuation (hematologic toxicity, non-hematologic toxicity, AE, dosing error, or other).

- The number of subjects with any reduction in the dose of the drug, and with a reason for the reduction of “hematologic toxicity”, “non-hematologic toxicity”, “AE”, “dosing error”, and “other”).

For PO dexamethasone the following summaries will be produced:

- The number of subjects with any dose modification, with 1, 2, 3, or ≥ 4 reported modifications, and with a reason for the modification of “hematologic toxicity”, “non-hematologic toxicity”, “AE”, “dosing error” and “other”).

By subject listings of record of study medication for each of IV dexamethasone and PO dexamethasone will be provided.

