4.3.3 Dose Delay or Interruption

If the dose of one drug in the regimen (ie, lenalidomide, dexamethasone or elotuzumab) is delayed or interrupted, the treatment with the other drugs may continue as scheduled. Subjects experiencing a 28 day delay in all study drugs lenalidomide, dexamethasone, and elotuzumab due to an adverse event(s) related to study treatment must be discontinued from study drug. Subjects experiencing delays unrelated to study therapy, for example due to radiation therapy may delay study treatment up to 42 days. Delays greater than 28 days must be discussed with the medical monitor.

Each cycle is 28 days. While dose delays or interruptions are permitted, the start of each cycle cannot be delayed and is fixed relative to Cycle 1 Day 1. Adjustments to the Cycle 1 Day 1 anchored schedule should not be performed. Missed doses should be skipped, not delayed, if not given within the allowed window.

Subjects may continue on study therapy even if components of the study therapy must be discontinued. For example, a subject on lenalidomide and dexamethasone may continue on study therapy even if dexamethasone must be discontinued for an adverse event. Likewise, a subject on

the investigational arm may continue on study therapy if elotuzumab must be discontinued for an adverse event or other reason. Patients are considered still on study therapy even if they continue solely on lenalidomide.

Please consult the BMS medical monitor or any questions regarding dose interruption or study therapy discontinuation.

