4.3.3.1 Elotuzumab

In Cycle 1 and 2, an elotuzumab dose that falls outside of the pre-specified window (-1 to +3 days) must be skipped.

In Cycles 3 and beyond, elotuzumab dosing may be delayed for up to 1 week. If unable to administer within 1 week, then the dose should be skipped and resumption of the elotuzumab continues per the protocol defined schedule.

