8.7 Topline Analyses

Outputs covering the following topics will be included in the top-line analyses:

Study conduct:

- Relevant protocol deviations (Table and Listing)

Subject population:

- End of Treatment Summary
- Accrual by Region
- Accrual by stratification factors at randomization
- Demographic Characteristics Summary
- IVRS Stratification Factors Summary
- Baseline Myeloma Characteristics Summary (SI units)
- Other Baseline Laboratory Measurements Summary
- Baseline Myeloma (Cytogenetics and FISH) Risk Factors Summary
- Time from Diagnosis to Randomization Summary
- Baseline Physical Measurements Summary

Extent of exposure:

- Number of Cycles Summary

- Elotuzumab Dose Intensity Summary
- Dexamethasone Dose Intensity Summary
- Lenalidomide Dose Intensity Summary
- Elotuzumab Delay Summary
- Elotuzumab Omission Summary
- Elotuzumab Infusion Interruption Summary
- Lenalidomide Reduction Summary
- Lenalidomide Interruption Summary

Progression free survival:

- Currentness of Follow-Up for PFS (IRC, ITT definition) Summary
- PFS (IRC, Primary Def.) Analysis
- Kaplan-Meier plot of PFS (IRC, Primary Def.)
- PFS (IRC, Primary Def.) Analysis Adjusting for Different Baseline Covariates
- PFS (IRC, Primary def.) Hazard Ratio and 95% CI in Subsets (Forest plot)
- PFS (IRC, ITT Analysis)
- Kaplan-Meier plot of PFS (IRC, ITT)
- PFS (IRC, ITT) Analysis Adjusting for Different Baseline Covariates
- PFS (IRC,ITT) Hazard Ratio and 95% CI in Subsets (Forest plot)
- Kaplan-Meier plot of PFS (Inv., Primary Def.)
- Kaplan-Meier plot of PFS (Inv., ITT.)
- Concordance of PFS between the IRC and investigator
- Concordance and Timing of PFS per IRC and Investigator
- Assessment of Censoring Distributions with Reverse Kaplan Meier Plot of PFS (IRC, Primary Def.)
- Assessment of Censoring Distributions with Reverse Kaplan Meier Plot of PFS (IRC, ITT Def.)

Tumor response:

- Best Overall Response (IRC)
- Best Overall Response (Inv)
- Best Overall Response (IRC) Modified for Subsequent Therapy
- Best Overall Response (IRC) Odds Ratio and 95% CI in Subsets (Figure)
- Cross Tabulation of Modified Best Overall Response per IRC and Investigator
- Time to First Response (IRC) Summary
- Kaplan-Meier Plot of Duration of Response (IRC)

Overall survival (only when interim PFS and ORR analyses are positive):

- Currentness of Follow-Up for Overall Survival Summary Overall Survival Analysis
- Overall Survival Analysis Adjusting for Different Baseline Covariates

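### Elotuzumab delays and omissions are judged by the gap since the previous infusion, not against the fixed Cycle 1 Day 1 schedule, so the delay and omission summaries can miscount in both directions

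*SAP*

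**What the plan says.** SAP 7.4.1.2 (Dose Modifications) bases an elotuzumab delay on "the number of days from the start date of the previous infusion to the start date of the current infusion". It gives three bands:

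- "being > 8 days and ≤10 days (if in cycles 1, 2 or first infusion of cycle 3")
- "> 15 days and ≤ 21 days (from second infusion of cycle 3 - cycle 19")
- "> 29 days and ≤ 35 days (from cycle 20 onwards")

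A longer interval is an omission. For the first band the wording is "If the interval between the two dosing dates for Elotuzumab is >10 days (in cycles 1, 2 or first infusion of cycle 3"); for the other two the limits are more than 21 and more than 35 days. Delay length is tabulated as 2-3 or 4-7 days. Delays and omissions recorded on the CRF go into by-subject listings whether or not the computed rule found them.

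Protocol 4.3.3 says that "the start of each cycle cannot be delayed and is fixed relative to Cycle 1 Day 1", and it forbids moving that schedule after a delay. Protocol 4.3.3.1 says that in Cycles 1 and 2 "an elotuzumab dose that falls outside of the pre-specified window (-1 to +3 days) must be skipped". From Cycle 3 it allows a delay of up to one week, after which the dose is skipped. The headers of Figure 3.1-2 and Table 4.3.1-1, however, show -1/+3 days for the day columns of all cycles.

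SAP 8.7 lists the "Elotuzumab Omission Summary" and a matching delay summary among the top-line outputs.

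**The concern.** The protocol defines lateness against a fixed calendar. The SAP measures a gap, and a gap depends on when both doses were given. An early previous dose makes the current one look later than it was, and a late previous dose hides lateness in the current one. The first infusion of Cycle 3 has a further problem: the SAP places it under the 10-day limit, while the protocol text allows a one-week delay from Cycle 3.

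At stake are the tables that describe how the investigational drug was delivered. They also attach CRF reasons to the computed events, so an omission that never happened may appear there with an unknown reason.

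**Working it through.** **Inputs.** Planned spacing *s* is 7 days in Cycles 1-2 and from Cycle 2 Day 22 to Cycle 3 Day 1. It is 14 days from then to Cycle 19 Day 1, and 28 days afterwards (Protocol 4.3.1). Permitted offsets from the planned day are -1 to +3 in Cycles 1-2 and up to +7 from Cycle 3 (Protocol 4.3.1, 4.3.3.1).

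With the previous dose at offset *p* and the current dose at offset *c*:

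- interval used by the SAP = *s* + *c* - *p*
- lateness against the protocol schedule = *c*

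**Reproducing the SAP limits.** With *p* = 0, spacing plus permitted lateness gives 7 + 3 = 10, 14 + 7 = 21 and 28 + 7 = 35. All three limits reproduce, but only for a previous dose on its planned day. The exception is Cycle 3 Day 1, where the protocol text gives 7 + 7 = 14, not 10.

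**Single intervals**

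| Situation | Interval (days) | SAP result | Against the schedule |
|---|---|---|---|
| Cycles 1-2: -1, then +3 | 7 + 3 + 1 = 11 | omission | given, in window |
| Cycle 3 Day 1: 0, then +4 to +7 | 11 to 14 | omission | given, within one week |
| Cycles 1-2: +3, then +3 | 7 | nothing | 3 days late |
| Two-weekly: +7, then +7 | 14 | nothing | 7 days late |
| Four-weekly: +7, then +7 | 28 | nothing | 7 days late |
| Cycles 1-2: -1, then +1 | 9 | 2-day delay | 1 day late |
| Cycles 3-18: +7, one dose skipped, then 0 | 28 - 7 = 21 | delay | one omission |
| Cycles 1-2: +3, one dose skipped, then -1 | 14 - 1 - 3 = 10 | delay | one omission |

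**Sequences** (a delay being 2 or more days late, the SAP's smallest category)

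- Cycles 1-2, every dose from Day 8 at +3: intervals 10, 7, 7, 7, 7, 7, 7. SAP: 1 delay. Schedule: 7.
- Cycle 3 Day 1 on time, next four doses at +7: intervals 7, 21, 14, 14, 14. SAP: 1 delay. Schedule: 4.
- Cycle 3 Day 1 and the next four doses all at +7, after an on-time Cycle 2 Day 22: intervals 14, 14, 14, 14, 14. SAP: 1 omission (14 > 10) and no delays. Schedule: 5 delays, no omissions.

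**Counts of possible offset pairs.** These show reach, not expected frequency.

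- Cycle 3 Day 1 is called omitted when *c* - *p* is 4 or more. For *p* = -1, 0, 1, 2, 3 that is 5 + 4 + 3 + 2 + 1 = 15 pairs, of 5 × 9 = 45 if -1 is allowed at that dose or 5 × 8 = 40 if not.
- A dose 2 or more days late is hidden when *c* - *p* is 1 or less. That holds for 3 + 2 = 5 of 25 pairs in Cycles 1-2. For two-weekly or four-weekly doses with offsets 0 to +7 it holds for 7 + 6 + 5 + 4 + 3 + 2 = 27 of 64.

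**Illustration of frequency, on assumed offsets.** Take the eight doses after Cycle 1 Day 1 up to Cycle 3 Day 1, all within -1/+3 and independent. Let *q* be the chance of -1 times the chance of +3. The chance of no -1 followed directly by +3 in *n* doses obeys a(n) = a(n-1) - *q* a(n-2), with a(0) = a(1) = 1. The chance of at least one false omission is 1 - a(8):

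- uniform offsets, *q* = 1/25: 1 - 0.743 = 26%
- 60% on the planned day, 10% on each other day, *q* = 0.01: 7%
- 80% on the planned day, 5% on each other day, *q* = 0.0025: 2%

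**The case against.** Several counterarguments carry weight.

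- **In-window delays.** A reader might infer that every 9-10 day interval between in-window doses is a false delay. The documents do not support that. The SAP chose a 2-3 day category, and in Cycles 1-2 a dose later than +3 must be skipped, so any delay tabulated there for a permitted dose is in window by design. A dose at +3 after an on-time dose is correctly shown as 3 days late. The interval basis creates a false delay only when the dose was less than 2 days late, which in Cycles 1-2 means -1 then +1: 1 of 25 pairs.
- **Frequency.** A reader might take the 26% as an estimate. It needs as many doses at +3 as on the planned day, which is extreme. The documents give no distribution of dosing days.
- **Later cycles.** Intervals of 22 or 36 days (-1, then +7) would also be false omissions, but only if the -1 in the table header applies after Cycle 2. With offsets 0 to +7 none arise from Cycle 3 Day 15 on.
- **Mitigation.** The listings show all CRF-reported delays and omissions, and the omission table has an 11-14 day band in which short gaps are visible. The SAP does speak of reported delays when it describes the delay counts, but the same text opens by defining a delay as computed from dosing records. The omission rule is likewise computed. The listings therefore do not correct the tables.

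This narrows the point. It does not remove the false omissions, the missed consecutive delays or the skipped doses counted as delays.

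**Conclusion.** The point stands as a minor one: the rule as written gives wrong counts. It rests only on the documents' own schedule and day arithmetic. The Cycle 3 Day 1 case is the clearest, since it needs no early previous dose; it assumes that the one-week allowance in the protocol text applies to that dose. Errors run in both directions and need not cancel. Their frequency in this trial is unknown.

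A reader might infer from the top-line status of these tables that efficacy conclusions are touched. They are not. PFS, ORR, OS, alpha and power do not use these flags. Dose intensity (SAP 7.4.1.3) is also unaffected, because it comes from cumulative dose over elapsed time.

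**What to change.** First reconcile the passages on the allowance. The protocol text gives -1/+3 days for Cycles 1-2 and up to one week from Cycle 3, the schedule table headers show -1/+3 for all cycles, and the SAP puts Cycle 3 Day 1 under the Cycle 1-2 limit. Which is intended is for the sponsor to state.

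Then amend SAP 7.4.1.2:

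- scheduled date = Cycle 1 Day 1 + 28 × (cycle - 1) + (planned day - 1)
- lateness = actual infusion date - scheduled date, tabulated in the existing 2-3 and 4-7 day categories
- omission = a scheduled dose with no infusion within the protocol's allowance for that cycle

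A delay should not be redefined as a dose outside the window. In Cycles 1-2 that would leave no possible delay and lose the 2-3 day information. Under the allowances in the protocol text, successive allowances do not overlap (+3 is before 7 - 1 = 6, and +7 is before 14 - 1 = 13), so each permitted infusion belongs to exactly one scheduled dose.

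The cost is one SAP definition and its derivation program, using dates already collected.

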4.3.4.3 Lenalidomide

Dose adjustments, as summarized below, are recommended for the management of NCI CTCAE Grade 3 and 4 toxicities for thrombocytopenia, neutropenia or other toxicities that are judged by the investigator to be related to lenalidomide. Information in Table 4.3.4.3-1 and Table 4.3.4.3-2 is based on current standard of clinical practice.

When Platelet Counts:	Recommended Course

 Fall to $< 30,000/\text{mm}^3$ Return to $\geq 30,000/\text{mm}^3$ 	Interrupt lenalidomide treatment; follow complete blood counts weekly. Resume lenalidomide at 15 mg, Days 1 - 21, once daily.
For each subsequent drop $< 30,000/\text{mm}^3$ Return to $\geq 30,000/\text{mm}^3$	Interrupt lenalidomide treatment. Resume lenalidomide at 5 mg less than previous dose, Days 1 - 21, once daily. Do not dose below 5 mg.

When Neutrophil Counts:	Recommended Course
Fall to $< 1000/\text{mm}^3$ Return to $\geq 1000/\text{mm}^3$ and neutropenia is the only toxicity	Interrupt lenalidomide treatment, add G-CSF; ^a follow complete blood counts weekly. Resume lenalidomide at 25 mg, Days 1 - 21, once daily.
Return to $\geq 1000/\text{mm}^3$ and if other toxicity	Resume lenalidomide at 15 mg, Days 1 - 21, once daily.
For each subsequent drop $< 1000/\text{mm}^3$ Return to $\geq 1000/\text{mm}^3$	Interrupt lenalidomide treatment. Resume lenalidomide at 5 mg less than previous dose, Days 1 - 21, once daily. Do not dose below 5 mg.

In case of neutropenia, consider the use of growth factors in subject management.

^a G-CSF = Granulocyte Colony-Stimulating Factor

Lenalidomide Dose Adjustments in Subjects with Renal Impairment

Since lenalidomide is primarily excreted via the kidney, adjustments to the dose of lenalidomide are provided based on the lenalidomide country prescribing information. The regimen of 21 day dosing every 28 days remains the same despite the dose reductions described below.

Table 4.3.4.3-3: Lenalidomide Dose Adjustments in Subjects with Renal Impairment^a	
Creatinine Clearance (CRCL):	Recommended Course
Moderate renal impairment (30 ≤ CRCL < 60 mL/min)	10 mg, every 24 hours
Severe renal impairment (CRCL < 30 mL/min, not requiring dialysis)	15 mg every 48 hours
End Stage Renal Disease (CRCL < 30 mL/min, requiring dialysis)	5 mg once daily. On dialysis days, dose should be administered following dialysis

^a Source: Lenalidomide USPI

Dose Adjustments During Treatment for Other Grade 3 and 4 Toxicities

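### The SAP's lenalidomide dose bands have no 20 mg level, so a subject whose lowest dose is 20 mg has no row in the lowest-level table

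*SAP*

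**What the plan says.** SAP 7.4.1.2, under lenalidomide dose reduction, sets five daily-dose bands. The top one begins "Dose level 0 or full dose (25 mg" and takes in 20.0 mg and above. The second is "Dose level -1 (15 mg): 12.5 mg to < 20.0". The remaining bands are 8.75 to below 12.5 mg (nominal 10 mg), 6.25 to below 8.75 mg (nominal 15 mg every 48 hours) and below 6.25 mg (nominal 5 mg).

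The section opens with "Reduction of Lenalidomide will be computed based on the actual dose received". A reduction is then counted "if the actual level of the administered dose is below the actual level of the administered dose in the previous instance". The term *actual level* is not defined for lenalidomide. The source is the daily total on the lenalidomide dosing page.

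The output is "The number and percentage of subjects with a dose reduction, and the lowest dose level achieved per subject", with categories -1, -2, -3 and -4 or below. On layout the SAP adds: "This table will be broken out by whether the subject started at the standard dose level or at the 10 mg dose level". Investigator-reported reasons are tabulated for calculated reductions. A by-subject listing shows every reported reduction, calculated or not.

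Protocol 4.3.4.3 (Table 4.3.4.3-2, neutropenia) says, for a first drop where neutropenia is the only toxicity, "Resume lenalidomide at 25 mg, Days 1 - 21, once daily". For each later drop it says "Resume lenalidomide at 5 mg less than previous dose, Days 1 - 21, once daily".

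**The concern.** The protocol's neutropenia steps produce a 20 mg dose that the SAP bands do not recognise as reduced. The lowest-level table has no level 0 category, so a subject whose lowest dose is 20 mg cannot be placed in it. What is at stake is a descriptive account of how often, and how far, lenalidomide was reduced in each arm. If *actual level* is also open to two readings, two programmers following the same text could report different numbers of subjects reduced.

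**Working it through.** **1. Reproduce the SAP cut-points.** The nominal daily doses in SAP 7.4.1.2 are 25, 15, 10, 7.5 (15 mg every 48 hours = 15/2) and 5 mg. Midpoints of neighbours:

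- (25 + 15)/2 = 20.0
- (15 + 10)/2 = 12.5
- (10 + 7.5)/2 = 8.75
- (7.5 + 5)/2 = 6.25

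All four match the printed limits. The SAP does not state a midpoint rule; it is inferred from this match. No 20 mg dose is among the nominal doses.

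**2. Is 20 mg reachable under the protocol?** Start at 25 mg. After a first isolated neutrophil drop, resume at 25 mg. After the next drop, resume at 25 - 5 = 20 mg. A further drop gives 20 - 5 = 15 mg. The capsule strengths in Protocol Table 4.1-1 (5, 10, 15 and 25 mg) can make up 20 mg, for example 15 + 5. The thrombocytopenia table goes straight to 15 mg, so among the two blood-count tables only the neutropenia one yields 20 mg.

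**3. Classify dose sequences with the SAP bands.**

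| Doses (mg) | SAP levels | Reductions, milligram reading | Reductions, level reading | Lowest level | Row in table? |
|---|---|---|---|---|---|
| 25, 25, 20 | 0, 0, 0 | 1 | 0 | 0 | No |
| 25, 25, 20, 15 | 0, 0, 0, -1 | 2 | 1 | -1 | Yes |
| 25, 15 | 0, -1 | 1 | 1 | -1 | Yes |
| 25, 15, 10, 5 | 0, -1, -2, -4 | 3 | 3 | -4 | Yes |

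The first sequence has no lowest-level row on either reading. The readings disagree only at the 25-to-20 mg step.

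**4. Consequence by reading.**

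- *Milligrams:* the first subject is in the number and percentage reduced, and the step is in the reason tabulation. The level rows then sum to fewer than the number reduced.
- *Defined levels:* the first subject is also missing from the number and percentage reduced. Every 25-to-20 mg step, including the one in the second sequence, is missing from the reason tabulation.

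**5. Who is affected.** In the subject-level rows, only subjects in the standard-dose panel whose lowest dose is 20 mg. Those who later reach 15 mg or less are placed in a row.

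**6. Check a 20 mg band.** With doses 25, 20, 15, 10, 7.5 and 5 mg, the new midpoints are (25 + 20)/2 = 22.5 and (20 + 15)/2 = 17.5; the lower three are unchanged. The sequence 25, 25, 20 then gives one reduction and a 20 mg row on either reading, and 25, 25, 20, 15 gives two reductions on either reading.

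**The case against.** The strongest reply is that the text favours milligrams. Reductions are computed from the dose received, the rule speaks of the administered dose, and the source is the daily total. SAP 7.4.1 also defines a subject's elotuzumab dose level as the actual dose, although it does not extend this to lenalidomide. The bands that follow the rule are weak support for the other reading, because the lowest-level rows need bands in either case. This stands. A reader might infer that the SAP undercounts lenalidomide reductions, but the documents support that only on the less natural reading. The missing row remains on both.

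A second reply is that other outputs show these subjects. The by-subject listing does retain reported reductions to 20 mg, but it gives no rate. Relative dose intensity and the interruption summary measure other things. Nor is every subject at 20 mg sure to appear as interrupted: Protocol 4.3.4 treats its criteria as general guidelines, and 4.3.4.3 has a separate route for other toxicities that steps down to an undefined next lower level.

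A third reply is that table details are left to a Data Presentation Plan (SAP 8.7). That plan might add a row, but SAP 7.4.1.2 as written lists the categories without one.

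**Conclusion.** The point holds, at low severity. The SAP bands label a protocol-defined reduced dose as full dose and leave it without a lowest-level row. The undercount of reduced subjects and of reasons is conditional on reading *actual level* as the defined bands.

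The number affected cannot be derived: neither document gives a neutropenia rate, and the protocol's dose criteria are guidelines. A reader might infer a bias between arms, a faulty topline table or an effect on the trial's conclusions. The documents do not support these. No direction of difference between arms follows from the text. SAP 8.7 lists a Lenalidomide Reduction Summary but does not show that it uses these rows. No efficacy test or adverse-event analysis uses the bands.

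The conclusion rests on 20 mg being recorded as a daily dose of exactly 20 mg, and on the neutropenia table being followed at least sometimes.

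**What to change.** In SAP 7.4.1.2, change the analysis bands only:

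- 25 mg: 22.5 mg or more
- 20 mg: 17.5 to below 22.5 mg
- 15 mg: 12.5 to below 17.5 mg
- lower bands unchanged

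Add a 20 mg row to the lowest-level table. Either label the rows by dose in mg, or renumber the levels and update the reported categories to match. State that a calculated reduction is any drop in these levels, which settles the meaning of *actual level*. Carry the same bands into the Data Presentation Plan.

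The cost is a few lines of SAP text and programming and one more table row. No new data are needed and no dosing instruction changes.
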